5.5 Patient Positioning and Treatment delivery

Patients will be positioned supine. Use of a rectal displacement balloon is optional but daily pretreatment prostate localization is required. Treatments will be carried out using Intensity Modulated Therapy with 6 MV or higher photons, using either a LINAC or tomotherapy.

5.6 Adverse Effects

5.6.1 Acute toxicity

Acute toxicities will be scored from the start of radiation to 90 days after completion of radiation. Early urinary and GI toxicity will be used to determine the number of fractions deliverable per week as described in Section 5.2. Toxicity grading will be based on a modified RTOG grading criteria (25) (see below).

	Grade 1	Grade 2*	Grade 3	Grade 4
Acute GU	Requiring no medication	Frequency of urination or nocturia, which is less frequent than every hour, dysuria, urgency, bladder spasm requiring local anesthetic. New obstructive symptoms requiring an alpha blocker	Frequency with urgency and nocturia hourly or more frequently/dysuria, pelvis pain or bladder spasm requiring frequent narcotic; gross hematuria with or without clot formation.	Hematuria requiring transfusion; acute bladder obstruction not secondary to clot passage, ulceration, or necrosis
Acute GI	Requiring no medication	Diarrhea requiring parasympatholytic drugs; mucous discharge not necessitating sanitary pads; rectal or abdominal pain requiring narcotic analgesics.	Diarrhea requiring parenteral support; severe mucous discharge necessitating sanitary pads, abdominal distension.	Acute or sub-acute obstruction, fistula or perforation; GI bleeding requiring transfusion; abdominal pain or tenesmus, requiring tube decompression or bowel diversion

* The pre-existing use of an alpha blocker for GU symptoms or of an antidiarrheal agent for GI symptoms does not constitute a Grade 2 toxicity

5.6.2 Late toxicity

Rectal toxicities

Late toxicities will be scored > 90 days from completion of radiation therapy. Late rectal complications will be used as the primary endpoint for dose-per-fraction escalation in this study, from which the maximum tolerated dose-per-fraction will be determined. The most common clinical syndrome of radiation proctitis is rectal bleeding, urgency/tenesmus, and loose bowel movements. Other, less common late complications include perforation, fistula, and bowel obstruction. Toxicity grading will be based on the FC-LENT grading criteria (see below). Patients will be monitored after treatment at regular intervals, and toxicity determined by history and physical examination. Greater than 40% Grade 2 or higher late rectal toxicity at 2 years will be considered dose limiting and the escalation rules are described in section 8

*FC-LENT rectal toxicity scale**

Grade 1	Symptoms not requiring medication
Grade 2	>4 stools daily above baseline for \geq 3 months; regular blood in stool for at least 6 months; pain not requiring narcotics; minor outpatient therapies (\leq 3 coagulations; enemas; steroids; antibiotics; opiates)
Grade 3	Dysfunction requiring non-surgical hospitalization for management; bleeding requiring transfusion and/or more than 3 coagulations; pain requiring narcotics
Grade 4	Dysfunction requiring surgery; perforation; life-threatening bleeding
Grade 5	Fatal complications

* pre-existing use of opiates does not constitute Grade 2 toxicity

Late GU toxicities

Late GU	Requiring no medication	Moderate frequency; generalized telangiectasia, intermittent macroscopic hematuria	Severe frequency and dysuria; severe generalized telangiectasia; frequent hematuria; reduction in bladder capacity (<150 cc)	Necrosis; contracted bladder (capacity <100 cc); severe hemorrhagic cystitis
----------------	-------------------------	--	---	--

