8.0 STATISTICAL CONSIDERATIONS

8.1 Treatment and Toxicities

This phase I/II trial will be conducted with three potential fraction size levels, with a potential of 50 patients per level (plus an additional 100 patients at MTS if permitted by the escalation rules) and an accrual rate of approximately 50 patients per year anticipated. This may estimate the maximum tolerated dose-per-fraction (MTD), defined as that fractionation schema that yields at most a 40% rate of late grade 2 rectal toxicity at 2 years. A modified LENT grading system for rectal toxicity will be used (28). That outcome is chosen for its clinical relevance; however, the extended follow-up makes the standard sequential designs impractically long at 3 years (one year accrual plus two years follow-up for each of three cohorts). We therefore use the simply modified class of prorated designs (R. Chappell and K. Cheung, Simple designs for phase I clinical trials of long-term toxicities, abstract presented at the 1998 meeting of the Society for Clinical Trials). Proration implies, for example, that two patients observed for one year each, constituting two patient-years of follow-up, are equivalent in information to one patient followed for two years. This implicitly uses the result of Teshima (29) that the cumulative incidence of late grade 2 rectal complications reaches 50% of the final value within twelve months of treatment and that the cumulative incidence of complications is approximately linear with time.

The prorated design will require the following conditions for escalation: at least twenty patient-years of observation; and a minimum of 5 patients followed for one year; and at most a 40% toxicity rate per two years (i.e., at most 2 toxicities per 10 patient-years) observed. Proration allows a great reduction in the overall time of the trial - with fifty patients accrued at a uniform rate over each year, the first two conditions will be satisfied after 15 months. Thus the entire study will take at most 45 months. The requirement of 5 patients being followed for one year is made for safety's sake. The situation may arise that the maximum 50 patients have been accrued at a particular dose-per-fraction step, but there is insufficient follow-up to allow escalation to the next dose-per-fraction step. Under these circumstances, additional patients may be accrued at the previous (next lower) dose-per-fraction level until follow-up conditions for the next escalation are met.

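### At the escalation decision most ongoing untreated rectal bleeding cannot yet have reached Grade 2, while its follow-up counts in full, so the observed toxicity rate is biased low

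*Combined protocol and SAP*

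**What the plan says.** Section 5.6.2 makes late rectal complications the primary endpoint for dose-per-fraction escalation and grades them on the FC-LENT scale. Timing is set by "Late toxicities will be scored > 90 days from completion of radiation therapy". The same section states: "The most common clinical syndrome of radiation proctitis is rectal bleeding".

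Grade 2 is a list of alternatives. Two depend on duration: "regular blood in stool for at least 6 months", and more than 4 extra stools a day for at least 3 months. Another, "minor outpatient therapies" (coagulations, enemas, steroids and others), has no duration. Nor does the Grade 3 criterion "bleeding requiring transfusion and/or more than 3 coagulations", or life-threatening bleeding at Grade 4. Symptoms that need no medication are Grade 1.

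Section 8.1 requires "at least twenty patient-years of observation", 5 patients followed for a year, and at most 2 toxicities per 10 patient-years. With 50 patients entering evenly over a year it expects that "the first two conditions will be satisfied after 15 months". It justifies proration by a cited result that "the cumulative incidence of late grade 2 rectal complications reaches 50% of the final value within twelve months of treatment", with roughly linear accumulation. Section 5.2 applies the same conditions to the 100-patient MTS expansion and has the rates updated every 6 months.

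**The concern.** A man who has bled regularly for five months without treatment is Grade 1 on this scale. He adds patient-years to the denominator and nothing to the numerator. Section 8.1 makes no allowance for this delay, and the delay works in one direction only: the level looks safer than it is.

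It bears most heavily on the first decision at each level, when few men have been followed for long. That decision opens the next dose-per-fraction level or the MTS expansion. Table 1 has Level II accruing from month 16, so men may already be in treatment there when delayed Level I events become countable. Fixing the follow-up clock at day 90 does not remove the problem, because the delay lies in the grade definition.

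**Working it through.** **Inputs.** 50 patients with entry time u uniform on 0–12 months (8.1); Level I, 22 fractions (Table 1) at 4 per week (1.5), i.e. 5.5 weeks or 1.26 months; late scoring from day 90, i.e. 2.96 months (5.6.2); 6-month and 3-month criteria (5.6.2). Assumed: onset uniform in time, and symptoms persist once begun.

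**1. The plan's 15 months.** The fifth patient enters at month 1.2 (5 × 12/50). The plan does not say when follow-up starts, so three clocks were tried.

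| Follow-up from | Patient-years at month 15 | Both conditions met |
|---|---|---|
| Registration | 37.5 | 1.2 + 12 = 13.2 months |
| End of radiotherapy | 32.2 | 1.2 + 1.26 + 12 = 14.5 months |
| Day 90 after radiotherapy | 20.2, but no patient has 12 months | 1.2 + 1.26 + 2.96 + 12 = 17.4 months |

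Fifteen months holds on the first two clocks and not on the third.

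**2. Scorable share of duration-only bleeding.** For A up to 12, the mean of max(0, A − u) is A²/24; for A between 12 and 24 it is A − 6.

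- *Month 15, the six months must fall after day 90.* Late time is 15 − 1.26 − 2.96 − u = 10.78 − u. Share = (10.78 − 6)²/10.78² = 22.8/116.2 = 20%. Only 4.78/12 × 50 ≈ 20 men have been followed long enough to score this way.
- *Month 15, onset before day 90 may count.* Time since radiotherapy is 13.74 − u. Share = (7.74²/24)/7.74 = 32%; about 32 men.
- *Month 17.4, day-90 clock.* Late time is 13.2 − u. Share = (7.2²/24)/7.2 = 2.16/7.2 = 30%, so 70% is not scorable.
- *3-month stool criterion, month 15, strict window.* 7.78²/10.78² = 52%.

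Over all three levels and 3 to 5 fractions per week, the month-15 shares are 18–23% (strict) and 30–35% (looser), so 65–82% is not yet scorable. On the strict reading the Level I share rises to 45% at month 21 and 64% at month 27.

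**3. Effect on the observed rate.** Even full two-year follow-up does not capture every duration-only onset: S = (24 − 2.96 − 6)/(24 − 2.96) = 0.71 (strict), or 18/24 = 0.75 (looser). Let p be the share of onsets that score only by the 6-month route and s the share scorable at the decision. Captured now is 1 − p + sp; captured at two years is 1 − p + Sp; the shortfall is one minus their ratio.

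| p (assumed) | Strict, month 15 (s = 0.197, S = 0.71) | Looser, month 15 (s = 0.32, S = 0.75) | Day-90 clock, month 17.4 (s = 0.30, S = 0.71) |
|---|---|---|---|
| 25% | 14% | 11% | 11% |
| 50% | 30% | 24% | 24% |
| 75% | 49% | 39% | 40% |

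Example, strict and p = 50%: 0.598/0.857 = 0.70, a shortfall of 30%. These figures isolate the duration delay; counting the first 90 days as follow-up would be a separate effect.

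**4. Effect on the decision.** Simulation, end-of-radiotherapy clock, month 15, discrete entries giving 31.7 patient-years, so the rule passes at 6 events or fewer (0.20 × 31.7 = 6.3). Take a 60% two-year onset rate, linear from the end of radiotherapy, with half of events duration-only. The two-year graded rate is 60% × (0.5 + 0.5 × 0.75) = 52.5%, above the 40% limit. The rule passes in 59% of runs. With no delay it passes in 33% at a 50% rate and 16% at a 60% rate, which bracket the fair comparison. If onsets begin only at day 90, the figures are 90% against 68% and 47%. At the month-21 update the first scenario still passes in 30% of runs, against 4% at a 60% rate with no delay.

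**The case against.** Several points against this have force.

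- *Bleeding has routes to Grade 2 or higher with no waiting time.* This stands. A reader might infer that all Grade 2 bleeding needs six months, or that most ongoing bleeding of any kind is uncounted. The documents do not support either: treated bleeding and Grade 3–4 bleeding score at once past day 90, and the untreated share is not given.
- *The six months need not fall wholly after day 90.* The text is silent. The looser reading lowers the unscorable share to about two-thirds and does not reverse the conclusion.
- *The limit concerns graded toxicity, not symptom onset.* This stands. Setting the month-15 count against all onsets would suggest shortfalls of 20, 40 and 60% for the three assumed shares; part of that never becomes Grade 2 within two years. The comparison in step 3 is with the two-year graded rate.
- *The cited incidence curve may already be on graded events.* This cannot be checked here. Yet even a curve that reaches half its final value at 12 months must lie below a straight line early on for any component that cannot score before month 6. At month 15 only 7 of 50 men have 12 months since radiotherapy, so early time is still over-credited.
- *There are safeguards.* Section 5.2 recognises possible early underestimation (as statistical fluctuation) and updates rates six-monthly, Section 5.1 lets late toxicity govern continued accrual, and Section 8.4 has the DSMB meet semi-annually. These recover part of the deficit, but may act after the next level has opened.

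**Conclusion.** The concern holds for bleeding that can reach Grade 2 only by duration. At about month 15, 65–82% of such ongoing bleeding is not yet scorable (about 70% at month 17.4 on a day-90 clock), while the patient-years count in full. The Grade 2 rate seen at the escalation decision is biased low. The direction is firm. The size is conditional: about 14, 30 and 49% below the two-year graded rate for assumed duration-only shares of 25, 50 and 75% on the strict reading, and about 11, 24 and 40% on the other two. All of this assumes even accrual, uniform onset and persistent symptoms.

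A reader might go on to infer that the trial will settle on too high an MTS. That is not shown, because later updates bring in much of the missing count. What is shown is a tilt toward opening the next level, or the MTS expansion, early.

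**What to change.** In Sections 5.2 and 8.1:

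1. State when the follow-up clock starts and whether symptom time before day 90 counts toward the duration criteria.
2. Record onset dates for regular rectal bleeding and for more than 4 stools daily above baseline.
3. At each escalation or MTS decision compute the rate twice: once with scored Grade 2 or higher events, and once also counting duration-pending symptoms ongoing at cutoff as provisional events. Remove a provisional event if the symptom resolves before the required duration.
4. Compare both rates with the existing limit. If they fall on opposite sides, defer the decision to the next six-monthly update.

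FC-LENT grading, the stated limit and final reporting stay unchanged. The provisional count is a parallel check because counting it outright against the same limit would over-count bleeds that resolve.

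The cost is protocol wording and two onset dates at visits where Section 7.3 already calls for toxicity notation. Some provisional events will resolve, so an escalation may occasionally be delayed by one update. In a simulation (end-of-radiotherapy clock, month 15, half of events duration-only, up to half of untreated bleeds transient), requiring the provisional rate to pass as well cut escalation at a true 60% rate from 88% to 34–44%. At a true 20% rate it cut escalation only from about 100% to 98–99%. These figures depend on the assumed shares.

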5.6.3 Serious Adverse Events

Serious adverse events (SAE) will be defined as all Grade 4 and Grade 5 toxicity. SAE'S will be phoned in to the Study Chairman at [contact] within one working day of the event. SAE's will be reported by the UW data managers to the DSMB and the Clinical Trials Monitoring Committee administrator within one business day of notification of SAE. These will also be discussed at regularly scheduled Disease Oriented Working Group meetings.

5.6.4 Quality of Life

Quality of life will be assessed by three separate questionnaires with special emphasis on bowel, bladder, and erectile function. Questionnaires will be performed prior to treatment, one , two and three years after completion of treatment. Overall quality of life will be assessed using The Spitzer Quality of Life Index (SQLI) (26). Bowel and bladder quality of life will be assessed using a questionnaire developed at Fox Chase Cancer Center (27). Erectile function will be assessed

using the International Index of Erectile Function Questionnaire (IIEF) (28). Data will be used to compare these patients to those who received conventional external beam radiation therapy.

5.7 Supportive Care

All supportive measures consistent with optimal patient care will be given throughout the study.

5.8 Duration of Therapy

Study treatment will be stopped if:

- The patient refuses the study treatment
- The patient's physician feels that continuing the study treatments would not be in the patient's best interest.
- The patient experiences severe treatment related toxicities as outlined in section 5.6.3.
- There is clear evidence of progressive disease.
- Treatment interruption more than 2 weeks.

All patients will be followed for disease status until progression and for survival until death.

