2.0 OBJECTIVES

2.1 To evaluate acute and long-term tolerances to dose-per-fraction escalation in the treatment of prostate cancer using optimized treatment delivery that employs IMRT, daily rectal balloon displacement, and transabdominal ultrasound localization of the prostate.

2.2 To clinically evaluate local tumor control and biochemical progression-free survival and metastasis-free survival.

2.3 To immunohistochemically measure the levels of p53, Bcl-2, and Ki-67 in pre-treatment diagnostic biopsy specimens from patients enrolled on this study and will analyze correlations between these markers and clinical outcomes (freedom from biochemical and metastatic failure) in univariate and multivariate fashion, taking conventional prognosticators such as stage, grade and PSA into account.

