6.0 MEASUREMENT OF EFFECT

6.1 General

The primary objectives of this study are to potentially establish the maximum tolerated hypofractionation intensity (or to determine whether the most hypofractionated schedule tested in this study is tolerated) for prostate cancer patients and to determine clinical response. Analyses for

clinical tumor control and PSA disease free survival will be performed when median 5-year follow-up is obtained. Data will be collected for efficacy evaluation as stated in section 6.2 and 6.3.

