6.2 Disease-free Status

Patients will be considered to be without biochemical recurrence if either the PSA is still declining or the PSA nadir has been reached and is below 1.0 ng/mL, there is no palpable or radiologic evidence of disease, PSA is not rising (defined as 3 successive increases in measured PSA levels each at least two months apart) and there is no evidence of metastasis. Patients not meeting these criteria will be judged to have a recurrence.

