6.3 Progressive Disease

Any patient with rising PSA on 3 successive serum measurements will be considered to have recurrent or progressive disease. The date of failure will be taken as midway between the nadir PSA date and the date of the first of the three rising PSAs.

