7.0 STUDY PARAMETERS

7.1 All pre-study laboratory tests must be done within 6 weeks of registration.

7.2 Patients will be evaluated weekly during radiotherapy by one of the clinical study investigators to assess acute toxicities and functional status

7.3. The follow-up schedule and evaluations are outlined below:

	Pre-study	Weekly during RT	4 weeks post-RT	3 months post-RT	Subsequent follow-up ^a
H & P	X		X	X	X
Weight	X	X	X	X	X
Performance status	X	X	X	X	X
PSA	X		X	X	X
CBC/platelets	X				
Toxicity notation	X	X	X	X	X
QOL assessment	X				X ^b
IPSS score	X		X	X	X

^a Subsequent follow-up will be every 3 months x 1 year post-treatment, every 4 months during years 2 - 3, every 6 months years 4 – 5 and then annually. Follow-up frequency can be increased if thought medically necessary by the treating physician

^b QOL assessment will be completed pre-treatment and at 12, and 24 and 36 months post-treatment.

* For patients for whom travel to the treating institution creates a hardship, scheduled follow-ups, with the exception of the 4 week and all annual follow-ups, can be conducted via telephone interview with PSA and any other indicated testing being carried out at a facility near to the patient.

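### Sections 5.8 and 6.3 together end required disease-status follow-up at PSA failure, so later local and metastatic events named in objectives 2.2 and 2.3 need not be recorded

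*Combined protocol and SAP*

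**What the plan says.** All references are to the combined protocol and SAP.

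- **Follow-up rule (5.8):** "All patients will be followed for disease status until progression and for survival until death".
- **Progression (6.3, Progressive Disease):** "Any patient with rising PSA on 3 successive serum measurements will be considered to have recurrent or progressive disease". No palpable, radiologic or metastatic finding is needed.
- **Efficacy data (6.1):** "Data will be collected for efficacy evaluation as stated in section 6.2 and 6.3".
- **Disease-free status (6.2):** one composite status. It combines the PSA criteria with the requirement that "there is no palpable or radiologic evidence of disease" and that metastasis is absent. Local failure and metastasis are not defined as events in their own right.
- **Objective 2.2:** "To clinically evaluate local tumor control and biochemical progression-free survival and metastasis-free survival".
- **Objective 2.3:** the biomarkers are to be correlated with "clinical outcomes (freedom from biochemical and metastatic failure) in univariate and multivariate fashion". Section 1.4 says the same.
- **Visits (7.3):** history and physical, PSA, performance status, toxicity and IPSS continue through year 5 "and then annually", with no stop at progression. Section 9.0 says that everything in this table is collected. The table has no row for imaging, local recurrence, metastasis or disease status.

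**The concern.** Objectives 2.2 and 2.3 concern events that can occur after a PSA failure, but the only sentence on how long disease status is followed stops at progression, and the only definition of progression is met by PSA alone. A site that follows the text has no duty to record a metastasis or local recurrence found later, even though it must still follow the man for survival.

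Follow-up for these events would thus end because of an event related to them. Metastasis-free survival and local control would tend to look better than they are, and the biomarker analysis would have fewer metastatic events. Events that were not recorded at the time may be hard to recover later.

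**Working it through.** **1. When required recording ends.** Section 5.8 says at progression. Section 6.3 says that three successive PSA rises are progression. Required recording of disease status therefore ends at PSA failure, if no clinical failure came first.

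**2. Whether another section requires it afterwards.** Section 6.1 refers back to 6.2 and 6.3, which yield one composite status. Sections 7.3 and 9.0 keep the visits and the table data going, but the table has no local or metastatic item. No section requires these events to be recorded after PSA failure.

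**3. Effect by endpoint.**

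| Endpoint | Needs disease status after PSA failure? | Affected |
|---|---|---|
| Biochemical progression-free survival (2.2), freedom from biochemical failure (2.3) | No | No |
| Composite DFS (8.2, defined in 6.2) | No, the first event ends it | No |
| Overall survival | No, followed until death | No |
| Local tumor control (2.2) | Yes | Yes |
| Metastasis-free survival (2.2) | Yes | Yes |
| Freedom from metastatic failure (1.4, 2.3) | Yes | Yes |

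**4. Direction of bias.** Assume that men with PSA failure have a higher hazard of local failure and metastasis than men without it. The documents give no figure for this. Censoring at PSA failure then removes the men at highest risk, and the estimates for those who remain are too favourable. If metastasis-free survival instead uses deaths in all men but metastases only up to PSA failure, a later metastasis counts only when the man dies, or not at all. The bias is again upward.

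**5. Men affected.** Inputs: the 15% five-year failure rate and 250 patients (8.3); 150 patients at the MTS (50 + 100, section 5.1). Treating all failures as PSA failures gives an upper figure at that rate.

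- 0.15 × 250 = 37.5, about 38 men.
- 0.15 × 150 = 22.5, about 22 men.
- At the 400 patients that 5.1 allows for: 0.15 × 400 = 60 men.

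These are men whose required disease-status follow-up ends by year 5. They are not missed events.

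**6. The plan's 79% power (8.3).** Inputs: 125 per group (median split of 250), 22% vs 8%, two-sided alpha 0.05/3 = 0.0167, z = 2.394.

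- Unpooled: SE = √(0.22×0.78/125 + 0.08×0.92/125) = 0.0443; 0.14/0.0443 − 2.394 = 0.77; power 77.8%.
- Arcsine: 78.6%. Pooled: 76.4%. Continuity-corrected: 70.5%.
- Schoenfeld, 37.5 events, hazard ratio 3: √(37.5/4) × ln 3 − 2.394 = 0.97; power 83.4%.

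The unpooled and arcsine forms come within about one point of 79%. The calculation uses the 15% overall failure rate, and 5.9 names the biomarker outcome as biochemical control, so the stopping point in 5.8 does not change it.

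**7. Metastatic failure as the biomarker outcome.** The documents give no metastasis rate. As an illustration, assume a five-year rate m, hazard ratio 3 and complete capture. The lower group rate p solves [p + 1 − (1 − p)³]/2 = m; for m = 5% the groups are 2.55% and 7.45%. Pooled two-proportion power at alpha 0.0167:

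| m (assumed) | Events in 250 | Power |
|---|---|---|
| 2% | 5 | 10% |
| 5% | 12.5 | 27% |
| 10% | 25 | 56% |

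Losing the metastases that occur after PSA failure would lower these further.

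**The case against.** **Visits continue.** Sections 7.3 and 9.0 continue examination, PSA and data collection with no stop at progression. A reader might infer from 5.8 that later metastases and local failures are never collected. The documents do not support that: a finding at such a visit could be noted. What remains is that nothing requires it, and the table has no item for it.

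**Section 5.8 does not cite 6.3.** The same section lists clear evidence of progressive disease as a reason to stop radiotherapy. That can hardly mean three PSA rises, because 7.3 schedules no PSA during radiotherapy and 6.2 wants rises at least two months apart. So 5.8 may have clinical progression in mind. This is a fair point about ambiguity. But 6.3 carries the heading Progressive Disease and is the only definition offered, so a site has no other to apply.

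**Follow-up runs until the third rise.** Although 6.3 backdates the failure, progression is known only at the third rise. With visits every 4 months in years 2–3 and every 6 months in years 4–5, the first and third rises are about 8 and 12 months apart. Disease status is still followed in that time. This stands, and events found then are captured, but it does not cover later ones.

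**Few metastatic events in any case.** Step 7 shows low power at modest metastasis rates even with full capture. This stands: amending 5.8 would not by itself make the metastatic biomarker analysis well powered. The bias in metastasis-free survival and local control remains.

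**The denominator is not firm.** Tissue participation is optional (1.5), so fewer than 250 may enter the biomarker analysis, while enrollment could reach 400. The counts in step 5 are therefore indicative.

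**Conclusion.** The concern holds in a limited form. Under the stated rules, local and metastatic events after PSA failure are not required to be recorded. This conflicts with parts of objectives 2.2 and 2.3 and sits uneasily with 7.3 and 9.0. The resulting censoring is informative and would tend to bias metastasis-free survival and local control upward and reduce metastatic events for the biomarker analysis. The direction rests on the assumption in step 4.

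The size is about 38 of 250 men, or about 22 of 150 at the MTS, by five years, if the 15% in 8.3 applies and the failures are PSA failures. The number of missed events cannot be stated, because the documents give neither a metastasis rate nor the share of metastases that follow PSA failure.

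A reader might also infer that objectives 2.2 and 2.3 cannot be answered at all. That goes too far. Their biochemical parts remain answerable, and local or distant failures found at or before PSA failure are within follow-up. Composite DFS, survival and the power in 8.3 are also untouched. Only the local-control and metastasis components are compromised.

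**What to change.** Three linked text changes:

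1. **Section 5.8:** state that biochemical status is followed until PSA failure; that local and metastatic status, with date and site of first event, continues to be recorded at the existing 7.3 visits regardless of PSA failure, until metastasis or death; and that survival is followed until death.
2. **Section 6.3:** state that PSA failure ends only the biochemical endpoint.
3. **Section 6.2 or a new subsection:** define local failure and metastasis as events separate from the composite, and add a matching item to the follow-up form and the 7.3 table.

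This changes data collection only and needs no added imaging. The cost is an amendment, two event definitions and a form item, plus longer data collection in about 15% of patients, who are already followed for survival. One limitation remains: without scheduled assessments, ascertainment is triggered by clinical findings, so event dates will be less uniform than those of PSA failure. The analysis should say so.
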